#### 13.5.5 Analysis of Exploratory Efficacy Endpoints

[REDACTED] endpoints up to [REDACTED] will be analyzed based on the methods described for secondary endpoints above for the [REDACTED]. Continuous endpoints up to [REDACTED] will be analyzed based on a [REDACTED] analysis that includes the fixed effects of treatment, visit, treatment by visit interaction, prior anti-TNF use (Yes/No), and Baseline value.

[REDACTED] endpoints measured once post-Baseline will be evaluated based on an Analysis of Covariance (ANCOVA) with terms for treatment, prior anti-TNF use, and subject specific Baseline values.

For [REDACTED], the following will be summarized descriptively based on the [REDACTED]  
[REDACTED] Changes in Baseline for the components of [REDACTED]

[REDACTED] will also be summarized descriptively.

Incidence of ADA, defined as the % of subjects with positive ADA based on the [REDACTED]  
[REDACTED], will be summarized and explored for correlation with various PK, safety and efficacy outcomes.

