8.6 Efficacy analyses

8.6.1 Analysis methods

Analysis of proportions

The Cochran-Mantel-Haenszel (CMH) test, incorporating prior anti-TNF use as a stratification factor, will be used to compare response rates of response-type variables between the 200 mg tildrakizumab and placebo within AS and nr-axSpA separately. In addition, the Mantel-Haenszel common risk (the response rate) difference between 200 mg tildrakizumab and placebo and the 95% confidence interval (CI) will be estimated. Should assumptions per the Mantel-Fleiss criterion not be satisfied, the comparison will be based on a Fisher's exact test after collapsing across levels of the stratification factor. In this case, the response rate difference and CI will be based on a normal approximation without considering stratification.

Mixed model repeated measures analysis of continuous endpoints

A mixed model repeated measure (MMRM) analysis will be performed. The SAS procedure PROC MIXED will be used. The preferred model will include the fixed categorical effects of treatment, visit, treatment-by-visit interaction, and prior TNF use (yes/no), as well as the continuous fixed covariate of baseline value. An unstructured matrix for the within-subject error variance-covariance will be used. The denominator degrees of freedom will be calculated according to the Kenward-Roger method.

In case of non-convergence with the unstructured matrix, other within-subject error variance-covariance matrices, such compound symmetry (CS), will be considered.

The model will provide least-squares mean estimates, standard errors, two-sided 95% confidence intervals and p-values (where applicable) for mean change at all time points between treatments (tildrakizumab vs. placebo).

Statistical Analysis Plan (SAP)

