8.6.4 Analysis of exploratory endpoints

The response-type endpoints (ASAS20/40 at other measurement time points, ASAS70, ASAS5/6 up to [REDACTED] and proportion of subjects who require adjustment of background therapy at Week 16 will be summarized with descriptive statistics. Continuous endpoints (change from baseline in PtGA of disease activity, Total Back Pain, Nocturnal Pain, Inflammation, BASFI, BASMI, BASDAI, ASQoL, ASDAS-CRP, ASDAS-ESR, MASES, SF-36, FACIT-fatigue, TJC46, SJC44, hsCRP, SPARCC MRI Index of Disease Activity Score of the SI Joints, SPARCC MRI Index of Disease Activity Score of the Spine, and Modified Berlin ASspiMRI) up to [REDACTED] will be analyzed based on a MMRM analysis that includes the fixed effects of treatment, visit, treatment by visit interaction, prior anti-TNF use (yes/no), and Baseline value. Due to placebo group switching to 200 mg Tildrakizumab at [REDACTED], the comparison between active drug and placebo will not be performed for the exploratory endpoints collected after [REDACTED]. Continuous endpoints after [REDACTED] be summarized descriptively.

Below is an example of the SAS code for the MMRM

[REDACTED]

For [REDACTED], the proportions of subjects who achieve ASAS20, ASAS40, ASAS70, and ASAS5/6, at each measured time point during [REDACTED] will be summarized by treatment

Statistical Analysis Plan (SAP)

group; change from Baseline in PtGA of disease activity, Total Back Pain, Nocturnal Pain, Inflammation, BASFI, BASMI, BASDAI, MASES, SF-36, FACIT-fatigue, TJC46, and SJC44 during Weeks 53 to 72 will be summarized descriptively by treatment group. In addition, there will be sub-groups of patients in Part 3 who either did or did not receive any new therapy for AS and these will be analyzed separately for ASAS20, ASAS40, and ASAS70.

All the exploratory analyses will be based on the FAS.

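### The exploratory MMRM fits one baseline slope for all visits, so the Week 24 difference can lose some precision if the slope changes over time; a baseline-by-visit term would protect against this at little cost

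*SAP*

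**What the plan says.** SAP 8.6.1 first gives the categorical terms of the repeated-measures model: "The preferred model will include the fixed categorical effects of treatment, visit, treatment-by-visit interaction, and prior TNF use (yes/no"). Baseline then enters as a single further term: "as well as the continuous fixed covariate of baseline value". The covariance is stated as follows: "An unstructured matrix for the within-subject error variance-covariance will be used". There is a fallback: "In case of non-convergence with the unstructured matrix, other within-subject error variance-covariance matrices, such compound symmetry (CS), will be considered". Treatment differences are reported at all time points.

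SAP 8.6.4 applies the model to the exploratory continuous endpoints, as an analysis "that includes the fixed effects of treatment, visit, treatment by visit interaction, prior anti-TNF use (yes/no), and Baseline value". Protocol 13.5.5 agrees: its model "includes the fixed effects of treatment, visit, treatment by visit interaction, prior anti-TNF use (Yes/No), and Baseline value". In all three places treatment is the only term that interacts with visit.

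SAP 8.6.4 also announces code ("Below is an example of the SAS code for the MMRM"), but the code is blacked out, so the written lists of terms are the only visible specification.

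**The concern.** An MMRM with a baseline main effect assumes that the regression of the outcome on baseline is the same at every visit. In a 24-week comparison this need not be true: a score often tracks its baseline closely at first and less closely later. If so, the single fitted slope is a compromise. Under an unstructured covariance it is a generalised least squares compromise, which gives most weight to visits with small residual variance, and those are usually the early ones.

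Week 24 is the end of the placebo-controlled period and the natural visit to quote. With about 45 subjects per arm in each cohort, modest chance imbalances in baseline are ordinary. If the slope at Week 24 differs from the common slope, part of the imbalance stays in the estimated difference, or is over-corrected. What is at stake is precision in the exploratory continuous endpoints.

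**Working it through.** **Plan's own figure.** There is none for these endpoints. The stated 80% power with 45 per arm (SAP 5) is for ASAS20. Its response rates, alpha and dropout are blacked out, so it cannot be reproduced, and it does not depend on the MMRM.

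**Inputs from the documents.** 45 per arm, 1:1 (SAP 5); fixed effects and unstructured covariance (SAP 8.6.1); placebo-controlled period to Week 24 (protocol contents list, 9.1.3.2).

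**Assumptions.** Six post-baseline visits at Weeks 4, 8, 12, 16, 20 and 24. This follows the dosing weeks in SAP 8.5.2, because the assessment schedule is not legible. All correlations and SDs are assumed, with baseline SD = 1 and complete data.

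**Formulas.** Let b be the vector of true baseline slopes by visit and S the residual covariance given baseline.

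- Slope at visit k = correlation with baseline × SD(k) / SD(baseline).
- Weights w = S⁻¹1 / (1'S⁻¹1). The common slope converges to b_c = w'b.
- Relative rise in Week 24 variance = (b24 − b_c)² × Var(baseline) / S24.

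Modelling change rather than the score subtracts 1 from every slope and leaves b24 − b_c as it is.

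**Three cases with the numbers in.**

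1. *Moderate decay*: correlation 0.3 + 0.5 × 0.8^lag, equal SDs. Slopes 0.700, 0.620, 0.556, 0.505, 0.464, 0.431; weights 0.41, 0.18, 0.10, 0.07, 0.09, 0.15; b_c = 0.596. S24 = 1 − 0.431² = 0.814. Rise = (0.431 − 0.596)² / 0.814 = 3.4%, after carrying full precision.
2. *Steep decay*: baseline correlation falling linearly from 0.7 to 0.3, SD rising from 1.0 to 1.2, correlation 0.9^lag between post-baseline visits. b24 = 0.3 × 1.2 = 0.36; b_c = 0.680. S24 = 1.44 − 0.36² = 1.310. Rise = (0.36 − 0.680)² / 1.310 = 7.8%.
3. *Very steep decay*: AR(1) with 0.8 per visit. b24 = 0.8⁶ = 0.262; b_c = 0.667. S24 = 1 − 0.262² = 0.931. Rise = (0.262 − 0.667)² / 0.931 = 17.6%.

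**Range.** The last column is the simulated Week 24 variance with a common slope divided by that with visit-specific slopes (45 per arm, 4,000 replicates).

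| Assumed structure | Slope, Week 4 → 24 | Weight on Weeks 4–12 | Common slope | Variance rise | Simulated ratio |
|---|---|---|---|---|---|
| Equal correlation 0.5 | 0.50 → 0.50 | 50% | 0.50 | 0.0% | 1.00 |
| Falling correlation, SD rising to 1.6 | 0.75 → 0.62 | 80% | 0.72 | 0.4% | 0.99 |
| 0.3 + 0.3 × 0.7^lag | 0.51 → 0.34 | 57% | 0.42 | 0.8% | 1.00 |
| 0.2 + 0.5 × 0.85^lag | 0.62 → 0.39 | 65% | 0.53 | 2.2% | 1.02 |
| 0.3 + 0.5 × 0.8^lag | 0.70 → 0.43 | 69% | 0.60 | 3.4% | 1.03 |
| 0.8 × 0.9^lag | 0.72 → 0.43 | 72% | 0.62 | 4.7% | 1.05 |
| Linear 0.7 to 0.3, SD to 1.2 | 0.70 → 0.36 | 94% | 0.68 | 7.8% | 1.08 |
| AR(1), 0.9 | 0.90 → 0.53 | 89% | 0.86 | 14.8% | 1.14 |
| AR(1), 0.8 | 0.80 → 0.26 | 77% | 0.67 | 17.6% | 1.17 |

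In subjects, (1 − 1/ratio) × 90 gives about 2 to 4 of 90 under moderate decay and 11 to 13 of 90 under AR(1). The standard error is about 1 to 2% larger under moderate decay and 7 to 8% larger under these AR(1) cases.

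**One realised trial.** A baseline imbalance of one standard error moves the Week 24 difference by the square root of the variance rise, in units of its own standard error: √0.034 = 0.18, √0.078 = 0.28, √0.176 = 0.42 in the three worked cases.

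**Cost of the extra term.** Six visits need five more parameters. Where slopes were equal or nearly so, the simulated ratio was 0.99 to 1.00, a cost of at most about 1% of variance.

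**The case against.** The strongest reply is that nothing in the documents shows that the slope changes. A falling correlation is not enough, because the slope is the correlation times an SD ratio. Entry requires a minimum BASDAI, which narrows the baseline spread, so post-baseline SDs may well rise. With correlation falling from 0.5 to 0.35 and SD rising from 1.0 to 1.4, the slope goes from 0.50 to 0.35 × 1.4 = 0.49 and the loss is nil. The result is also sensitive: for a fall from 0.7 to 0.3, varying only the assumed SDs and between-visit correlations moves the loss between 3% and 27%. This stands, and it makes the point conditional.

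Two further limits also stand. The primary and secondary efficacy endpoints are binary and do not use the MMRM. And an endpoint with a single visit before the placebo switch has nothing to pool; the protocol uses ANCOVA for endpoints measured once. MRI may be such a case, but its timing is blacked out. A reader might infer that every continuous endpoint is affected; the documents do not support that.

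The compound-symmetry fallback answers less. It removes the early-visit lean but still uses one slope. In the linear 0.7 to 0.3 case the plain average slope is 0.541, and (0.36 − 0.541)² / 1.310 = 2.5% remains.

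The SAP calls this the preferred model and the code is not visible, so an interaction in the code cannot be excluded. The written lists do not contain one.

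**Conclusion.** The point holds as a low-cost improvement to an exploratory analysis. As written, the model has one baseline slope, which under the unstructured covariance usually leans to the early visits. The Week 24 variance then rises by about 0% with stable slopes, 2 to 5% under moderate decay and about 8 to 17% under steep decay. These figures rest on assumed correlations, SDs and six visits.

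A reader might infer a biased Week 24 comparison, or a definite loss of precision. Neither is supported. Randomisation keeps the complete-data comparison unbiased on average, and the loss arises only if the Week 24 slope differs from the common one, which the documents do not let anyone establish. The primary CMH test and the 80% power are unaffected. The reason to act is the asymmetry: a cost of at most about 1% against a possible loss of several percent.

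**What to change.** Add a baseline-by-visit interaction to the MMRM fixed effects in SAP 8.6.1 and 8.6.4, for exploratory continuous endpoints with more than one visit before the placebo switch, or give a reason for assuming a constant slope. It uses data already collected and changes one term in the model statement.

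The cost is one extra parameter per additional visit (five with six visits), and at most about 1% of variance if the slope is constant.

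SAP 10 records that the study was terminated, and the methods summary at the front of the SAP file describes the model in the past tense. If the database is already locked, the term can be fitted as a supplementary analysis and described and justified in the CSR, as SAP 1 requires for departures from the plan.

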8.6.1.1 Multiplicity

Not applicable.

8.6.2 Analysis of primary efficacy endpoint

The primary efficacy variable is ASAS20 at [REDACTED] ASAS20 will be analysed with CMH test as described in [REDACTED] for AS and nr-axSpA cohorts separately. Early withdrawals and any subjects with ASAS20 undeterminable at [REDACTED] will be classified as non-responders. Subjects who fail to show minimal response to treatment (defined as [REDACTED] improvement from Baseline in total back pain or inflammation) at [REDACTED] may have their background medications adjusted according to the maximum permitted daily dose described in the protocol and continue in the study. Any subject requiring these adjustments will be counted as a non-responder for the primary analysis.

The sample SAS codes are:

[REDACTED]
[REDACTED]
[REDACTED]

To assess the robustness of the primary efficacy analysis, sensitivity analysis will be repeated with the PPAS.

Subgroup analysis will be performed for each of the following subgroup variables:

- Prior anti-TNF use (Yes/No)
- Baseline weight (≤ 90 kg, > 90 kg)
- Age (< 65 , ≥ 65)
- Gender
- Methotrexate use (Yes/No)

The sample SAS codes for anti_TNF subgroup analysis are:

[REDACTED]
[REDACTED]
[REDACTED]
[REDACTED]
[REDACTED]
[REDACTED]

Estimates of the difference between the treatment groups, along with the [REDACTED] (but no p-value needed), will be presented for each defined category of each subgroup variable.

Statistical Analysis Plan (SAP)

If sample size for a category of a subgroup factor is too small, the analysis for that subgroup may not be performed.

The primary purpose of the subgroup analyses is to check for consistency of results across factors of interest.

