### 9.2.1 Risk/Benefit and Ethical Assessment

As this is the first study in patients with AS and nr-axSpA the benefits of tildrakizumab in these patient populations remains uncertain. Given that efficacy benefits were reported for subjects with concurrent PsA in the completed Phase 2b study in PsO (Protocol PO5495), there is an expectation that subjects treated with tildrakizumab may experience improvement in AS and Protocol CLR\_16\_22 Version [REDACTED] (Final)

nr-axSpA disease activity as these conditions are related to PsA. However, the study design allows early identification of subjects who have not received a minimum level of improvement at [REDACTED] to enable the Investigator to adjust background therapy or remove IMP and initiate other treatment at their discretion.

The study has also been designed to minimize potential risks to subjects; all subjects will undergo Screening procedures aimed at reducing the likelihood and impact of any such risks. Radiographs used for inclusion/exclusion at Screening will be read centrally to ensure consistent assessment across sites. In addition, regular safety monitoring during the treatment period for all subjects will ensure that any unanticipated effects of study participation are identified promptly and managed appropriately. In view of the long half-life ( $T_{1/2}$ ) of tildrakizumab at doses previously studied, subjects will continue to be monitored throughout a [REDACTED] period following the [REDACTED] visit, during which no active IMP will be administered and subjects can receive other treatments at the Investigator's discretion.

In addition, an independent DSMB will review selected data across the study. The DSMB in conjunction with the Sponsor is empowered to make recommendations regarding continuation, termination or modification of the study, as appropriate.

Overall, based on data from non-clinical and clinical studies of tildrakizumab to date and the risk minimization strategies discussed above, the risk:benefit profile of the current study is considered acceptable.

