**9.3.6 Continued Study Participation**

The Investigator must determine the primary reason for the subject's premature discontinuation of investigational treatment and record this information on the treatment disposition eCRF page. The Investigator and study staff must discuss with the subject, the subject's continued participation in the study and request subjects to continue attending follow-up study visits according to the study visit schedule.

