#### **10.6 Concomitant Therapy**

The following restrictions will apply to all subjects during the study.

Concomitant medications limited throughout the study [REDACTED]

- Analgesics: Acetaminophen may be used by the subject [REDACTED] except within [REDACTED] before a scheduled study efficacy evaluation.

Concomitant medications will be limited during Part 1 of the study [REDACTED] as follows:

- NSAIDs: For subjects receiving NSAIDs [REDACTED] the subject must be on a stable dose for [REDACTED] prior to [REDACTED] of IMP and be expected to maintain a stable dose for the [REDACTED] of the study, unless change in dosage is required due to toxicity. Stable dose [REDACTED] is defined as subjects taking an NSAID on average [REDACTED] per week for the [REDACTED] prior to [REDACTED] g.

- Corticosteroids: Subjects taking oral corticosteroids [REDACTED]  
[REDACTED]
- DMARDs: Subjects taking either MTX [REDACTED] or [REDACTED] [REDACTED]  
[REDACTED] must remain on a stable dose, unless a decrease in dose is required because of toxicity or intolerance. Other [REDACTED] and oral MTX [REDACTED] be changed to [REDACTED] dosing during the period of observation. Subjects [REDACTED] MTX and [REDACTED].

Tapering of any of these concomitant medications during the study is allowed only if there is toxicity (accompanied by recording of an AE on the eCRF); otherwise the dosage must remain the same throughout Part 1 of the study. Adjustment of these concomitant medications is permitted throughout Part 2 (Week 25 to 52) as needed per Investigator discretion and therapeutic needs of the subject, or if the subject does not show minimal response to treatment (defined as < 10% improvement from Baseline in pain [assessed by Total Back Pain VAS 0 to 100] and inflammation [assessed using the last 2 stiffness assessments in the BASDAI]) at Week 16.

For subjects receiving non-drug therapy (including but not limited to physical therapy, massage, diet, exercise, emollients, and joint taping), this must be stable for the 4-week period prior to IMP initiation through to the end of Part 1.

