### 13.4.2 Primary Efficacy Endpoint

The primary efficacy endpoint is the proportion of subjects who achieve ASAS20 at Week 24.

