6.6 Protocol deviations/violations and exclusions from analysis sets

All deviations and exclusions of subjects from analysis sets will be identified at the Classification

Statistical Analysis Plan (SAP)

Meeting just prior to study unblinding, through clinical review input provided by Sponsor, using the following sources of information:

- Supportive subject listings, provided by the ██████ lead statistician ahead of the Classification Meeting, based on data recorded on the eCRF.
- Protocol Deviation Logs, provided by ██████ Medical/Clinical.

Further, deviations from the protocol will be classified as major/minor or key/non-key depending on documentation in ██████

The protocol deviations that will lead to subject exclusion from the PPAS are listed as below. It is possible that unexpected deviations will arise as the study moves forward. Therefore, more deviations may be added to the list later. Prior to database lock, a classification meeting will be conducted to identify subjects to be excluded from PPAS, and the decision will be documented in a separate file.

- Subject with BASDAI ██████ at Screening or Response to the BASDAI question 'How would you describe the overall level of AS neck, back or hip pain you have had?' of ██████ on the VAS ██████ at Screening
- Non-compliance with study treatment ██████)
- Disallowed concomitant medications
- Treatment error - at least one dose of randomized treatment and one dose of incorrect treatment were administered to a subject.

Statistical Analysis Plan (SAP)

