7.2 Handling of missing data and outliers

7.2.1 Missing data analysis methods

In the primary analysis, ASAS20 response rate at [REDACTED], missing values will be handled by setting the ASAS20 value to nonresponsive. This approach will be used for all “response-type” endpoints (ASAS40, ASAS70, and ASAS5/6) at all time points.

For a composite “response-type” endpoint (such as ASAS[REDACTED]), if values in any of the components at a time point are missing, the component variables that are not missing will be used to determine the response status. If one cannot determine the response status in the presence of missing components, then the composite response-type endpoint status is considered “non-response” for that time point.

For the BASDAI, BASMI, BASFI, MASES, SF-36, and FACIT instruments, rules suggested by the developers of these will be followed in calculating scores when individual question/items may be missing.

Details on handling missing data are outlined in [REDACTED].

In general, missing values in any of the endpoints will not be imputed when summarizing these endpoints using descriptive statistics.

In addition, missing values for safety endpoints will not be imputed.

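### The primary responder rule fails sanctioned background adjustments but does not score unsanctioned or rescue therapy in Part 1, so like cases in the FAS can count oppositely

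*SAP*

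**What the plan says.** Protocol 13.4.2 sets the endpoint: "The primary efficacy endpoint is the proportion of subjects who achieve ASAS20 at Week 24". Readable text gives these routes to non-response:

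- **Withdrawal or no result.** SAP 8.6.2 opens its rule with "Early withdrawals and any subjects with ASAS20 undeterminable at" the primary visit. SAP 7.2.1 adds that "missing values will be handled by setting the ASAS20 value to nonresponsive".
- **One therapy change.** SAP 8.6.2 allows background medication to be adjusted in subjects without minimal response, then states: "Any subject requiring these adjustments will be counted as a non-responder for the primary analysis". The methods documentation headed 16.1.9 repeats this rule in the past tense.

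For Part 1, Protocol 10.6 permits tapering of background therapy only for toxicity; "otherwise the dosage must remain the same throughout Part 1 of the study". It also provides for adjustment when minimal response is absent at Week 16. There, and in the synopsis, lack of minimal response refers to pain *and* inflammation. SAP 3.1 and 8.6.2 say pain *or* inflammation.

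Rescue medication is a per-protocol (PPAS) deviation in Protocol 13.3.2 and SAP 6.2. SAP 6.6 lists "Disallowed concomitant medications" among the PPAS exclusions. The FAS (SAP 6.1) keeps every randomized subject with at least one dose.

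On stopping IMP, Protocol 9.1.1 and SAP 3.1 send the subject to an End of Treatment assessment and then to washout. Protocol 9.3.6 tells sites to "request subjects to continue attending follow-up study visits according to the study visit schedule". Protocol 9.2.1 describes a monitored period after a blacked-out visit, "during which no active IMP will be administered and subjects can receive other treatments at the Investigator's discretion".

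**The concern.** The plan already treats escalation of background therapy as failure on this endpoint, but ties that to one sanctioned provision. A subject who breaks the Part 1 stability rule has a protocol deviation. That may cost PPAS membership, but no readable text changes the subject's FAS outcome.

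The four ASAS20 domains (SAP 4.1) are patient-reported: global assessment, back pain, function and stiffness. They are open to symptomatic treatment. Protocol 10.6 recognises this by barring acetaminophen shortly before efficacy evaluations. SAP 8.6.4 recognises it again in Part 3, where ASAS20, ASAS40 and ASAS70 are analysed separately by receipt of new therapy. The Part 1 primary analysis has no equivalent.

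At stake is the meaning of the primary comparison. If the arms differ in unsanctioned use, part of the Week 24 difference reflects added therapy, and the one named sensitivity analysis does not test for it.

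**Working it through.** **Step 1: apply the readable rules to typical subjects.**

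| Subject in the FAS | Rule that applies | Primary outcome |
|---|---|---|
| Background therapy raised under the Week 16 provision; ASAS20 met at Week 24 | SAP 8.6.2, adjustment sentence | Non-responder |
| Same increase without sanction (other time, or criterion just missed); ASAS20 met | None in FAS; possible PPAS exclusion | Responder |
| Disallowed drug taken, dosing suspended then resumed (Protocol 9.3.5); ASAS20 met | None in FAS; PPAS exclusion | Responder |
| Falls short in one minimal-response domain only, therapy raised; ASAS20 met | SAP *or*: sanctioned. Protocol *and*: deviation | Depends on the document |
| No Week 24 value, any reason | SAP 7.2.1, 8.6.2 | Non-responder |
| IMP stopped, still in study, Week 24 value obtained | Depends on the undefined term early withdrawals | Cannot be determined |

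Rows 1 and 2 are the core inconsistency. Row 4 shows that even the covered group is unsettled.

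**Step 2: the plan's own figure.** SAP 5 gives about 45 per arm in each cohort with 80% power, accounting for futility. This cannot be reproduced, because both response rates, the significance level and the dropout rate are blacked out. Assuming two-sided 0.05, no dropout, no futility stop and a placebo rate of 20% to 40%, 45 per arm has 80% power for a difference of about 28 to 29 points.

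**Step 3: weight of one subject.** 1/45 = 0.022, or 2.2 points on that arm's rate.

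**Step 4: illustration.** Assume 14/45 (31.1%) on placebo against 27/45 (60.0%) on tildrakizumab when every subject on unsanctioned therapy is scored as a failure. Use the unstratified test z = (p1 − p0)/√[2p̄(1 − p̄)/45]. With p̄ = 41/90 = 0.456, z = 0.289/0.105 = 2.75 and p = 0.006. Then count k such subjects as responders instead:

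| Extra placebo responders | Extra tildrakizumab responders | Difference (points) | p |
|---|---|---|---|
| 0 | 0 | 13/45 = 28.9 | 0.006 |
| 2 | 0 | 11/45 = 24.4 | 0.020 |
| 4 | 0 | 9/45 = 20.0 | 0.058 |
| 0 | 2 | 15/45 = 33.3 | 0.0015 |
| 0 | 4 | 17/45 = 37.8 | 0.0003 |
| 2 | 2 | 13/45 = 28.9 | 0.006 |

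Power at the rates in the first three rows is 0.80, 0.65 and 0.48. The counts are assumptions; the documents give no rate of unsanctioned use.

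**Step 5: does the PPAS repair this?** Take the row with four extra placebo responders, and suppose only those four are excluded. Placebo becomes 14/41 = 34.1% and the difference 60.0 − 34.1 = 25.9 points. Scoring them as failures gives 28.9, and counting them as observed gives 20.0. The PPAS drops these subjects from the denominator, so it estimates a third quantity.

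**The case against.** **Key text is not visible.** The mandatory discontinuation list and the suspension list in Protocol 9.3.5 are blacked out, as is the SAS code in SAP 8.6.2. Disallowed therapy may force IMP discontinuation and so lead to non-response. Protocol 15.1 adds that deviations may lead to withdrawal and make a subject non-evaluable. The supplied protocol is dated 14 June 2017, while the SAP cites V3.0 of 19 March 2018. These caveats stand. They do not supply a scoring rule in the readable SAP, and Protocol 9.3.5 lets dosing resume after a medication-related suspension, so such a subject can reach Week 24.

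**Keeping deviators' observed outcomes in the FAS is a recognised strategy.** True, and a plan that did so throughout would be coherent. This one scores sanctioned escalation as failure and unsanctioned escalation as observed, without giving a reason.

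**Subjects who stop IMP.** A reader might infer that someone who stops IMP and is treated otherwise will count as a responder. The documents do not support that. The End of Treatment and washout route would usually leave no Week 24 value, and hence non-response. The follow-up visits in Protocol 9.3.6 may simply be the washout visits, and the synopsis wording on withdrawals and incomplete data is broad. What remains is an undefined term and two sections to reconcile.

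**Conclusion.** The point holds in a limited form. Besides early withdrawal and missing or undeterminable ASAS20, the only therapy change scored as non-response in the FAS is the permitted adjustment. Unsanctioned or rescue therapy in Part 1 with an evaluable Week 24 result can count as success. This is an inconsistency in the plan's own rule and should be corrected.

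Its size is 2.2 points per affected subject in an arm, assuming about 45 per arm. Two to four affected responders in one arm only would move the difference by 4.4 to 8.9 points; equal numbers in both arms would leave it unchanged. How many would occur is unknown.

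Two further inferences should be resisted:

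- **That the bias runs towards no effect.** This presumes more unsanctioned use on placebo. More use on tildrakizumab would enlarge the difference.
- **That these shifts can be judged against the 12% futility threshold.** That threshold (SAP 8.9) is a between-arm difference at Week 16 in 30 subjects. Therapy started after Week 16 cannot affect it, and a shift in one arm's rate is not the same quantity.

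**What to change.** 1. Extend the SAP 8.6.2 sentence. For ASAS20 and ASAS40 at Week 24, a subject is a non-responder if, in Part 1, they started or increased disallowed or background therapy for axial disease, sanctioned or not, and that use could affect the Week 24 assessment. Name ASAS40 explicitly, because SAP 8.6.3 carries over only the CMH method.
2. Before unblinding, fix under blind the qualifying drug classes and the duration and timing window, so that brief early use does not void a genuine Week 24 response. Dose reductions for toxicity stay unaffected.
3. Report the FAS result with observed outcomes for unsanctioned use as a sensitivity analysis. If the analysis has already been run, as the past-tense methods text suggests, keep the executed rule as primary and add the extended rule as a labelled sensitivity analysis.
4. Define early withdrawals, stating whether IMP discontinuation before Week 24 is included.
5. Reconcile Protocol 9.3.6 with Protocol 9.1.1 and SAP 3.1, and the *and*/*or* wording of minimal response. Which clinical wording is intended is for the sponsor to state.

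The cost is SAP wording, one extra table and a blinded medication review. SAP 7.2.2 and 8.4.4 show that medication dates are available. No readable section confirms that dose changes and indication are recorded, so that needs checking. Response rates may fall somewhat in either arm.
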